### 10.6.1 Pharmacodynamics

All pharmacodynamic endpoints will be summarized by visit and treatment group including the ratio to baseline for each treatment along with their associated confidence intervals.

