## 16 Appendix 3 – Assessment Schedules

**Table 16-1 Assessment Schedule (Year 1)**

Period	Screening	Treatment Period (Year 1)													
		Day				Month									
		-30 to -1	1	8	30	60	3	4	5	6	7	8	9	10	11
Visit Window (days)				±2	±3	±3	±5	±5	±5	±5	±5	±5	±5	±5	±5
Informed consent/Genetic consent 	x														
Inclusion/Exclusion criteria	x	x													
Demography/Medical History	x														
Physical Exam	s														
Height and Weight	x														
Vital signs	x	x		x					x						x
12-lead ECG	x														
HIV, Hepatitis B, Hepatitis C	s														
Serum Pregnancy and FSH	x														
Urine Pregnancy - WOCBP only		s		s		s		s		s		s		s	
Hematology	x	x				x		x		x		x		x	
Chemistry	x							x							x
Urinalysis	x														
PT/INR, aPTT	x	x		x		x		x		x		x		x	
PK  and Free FXI / Total FXI 		x		x		x		x		x		x		x	
Antidrug antibodies (ADA) 		x		x		x		x		x		x		x	
Factor XI Coagulation Activity 		x		x		x		x		x		x		x	
Exploratory biomarkers 	x														x
Genetic sample 	x														
EQ-5D-5L and ACTS PROs 	x							x							x
Telephone call visit only			x												
Study drug s.c. administration 		x		x	x	x	x	x	x	x	x	x	x	x	x
Study drug p.o. accountability 			x	x	x	x	x	x	x	x	x	x	x	x	x
Injection site inspection 		x		x	x	x	x	x	x	x	x	x	x	x	x
Concomitant medications	x								x						
AE assessment								x							

 The genetic informed consent is for an optional sub-study; the genetic sample can be collected at any time after the optional genetic informed consent is obtained

 Only collected from patients assigned to abelacimab

 May be collected in a subset of patients

 Patients assigned to abelacimab only; Dose can be administered at in-clinic or in-home visits by medically qualified, un-blinded study staff or designees as locally permitted. If administered in-home, assessments for concomitant medications, AEs, and other changes in health status will be conducted by sites via telephone or video call as locally permitted

 Patients assigned to rivaroxaban only; Accountability can be assessed at in-clinic visit or via virtual (e.g. video call) visit as appropriate and locally permitted

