## 2.8. Pharmacokinetic/Pharmacodynamic and Other Variables

- Trough abelacimab plasma concentrations at indicated time points
- Activated partial thromboplastin time (aPTT), free factor XI (FXI), and total FXI at indicated time points
- Percentage of abelacimab-treated patients who develop anti-drug antibodies (ADAs)
- Assess the impact of ADA development to safety, efficacy, PK and PD responses
- Exploratory coagulation parameters which may include, but not limited to, [REDACTED]  
[REDACTED]
- Exploratory evaluation of the association between [REDACTED]  
[REDACTED]

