#### 5.1.2. Screening / Baseline Period

For all patients, the screening period is defined as the period from informed consent to randomization. For some variables, data from more than one assessment within the screening Period can be collected prior to randomization.

The baseline value for a variable is therefore defined as the last non-missing value collected before randomization.

Assessments carried out on day of randomization are considered to have taken place before randomization if the corresponding times have not been recorded.

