### 5.1.3. Treatment Period

Data collected on the day of first dose will be assigned to the Treatment Period if the time (HH:MM) of data collection and time (HH:MM) of first dose of treatment are both recorded, and the data collection time is on or after the time of first dose of treatment. Otherwise, the assessment will be assigned to the screening / baseline period. If the time (HH:MM) of data collection is not recorded but the protocol and / or eCRF includes an instruction to the effect that all Day 1 assessments are to be performed prior to the first dose of treatment or randomization, the data collected at Day 1 will be assigned to the screening / baseline period, otherwise it will be assigned to the Treatment Period.

The Treatment Period is defined as the period from the date of the first dose of treatment up to and including the EoT date as defined in Section 3.1.

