### **6.8. Pharmacokinetic/Pharmacodynamic Assessments**

A listing of PK blood sample collection times and Plasma concentrations will be presented for detail analyte(s) from protocol separately for all patients for the Pharmacokinetics Analysis Set.

Pharmacokinetic concentrations will be summarized for the Pharmacokinetics Analysis Set for each timepoint by treatment group and overall using protocol scheduled times and appropriate summary statistics.

See Section [5.2.4](#) for the handling of Plasma concentrations that are BLQ.

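### SAP 5.1.2 ties baseline to randomization, so when both times are recorded it rejects the only pre-treatment FXI sample, while SAP 5.1.3 treats that sample as baseline data

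*SAP*

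**What the plan says.** SAP 5.1.2 ends screening at randomization ("the screening period is defined as the period from informed consent to randomization") and then defines baseline: "The baseline value for a variable is therefore defined as the last non-missing value collected before randomization". It adds one exception: "Assessments carried out on day of randomization are considered to have taken place before randomization if the corresponding times have not been recorded".

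SAP 5.1.3 uses a different anchor. A value from the day of first dose goes to the Treatment Period when both clock times are available and "the data collection time is on or after the time of first dose of treatment"; otherwise it belongs to the screening/baseline period. An untimed Day 1 value goes to the screening/baseline period if the protocol or eCRF requires Day 1 assessments before dosing or randomization, and to the Treatment Period if not.

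In protocol Table 16-1, PK, free FXI, total FXI and ADA are first marked on Day 1, with nothing at screening. Their footnote reads "Only collected from patients assigned to abelacimab". Hematology, PT/INR, aPTT and vital signs are marked at screening and on Day 1, without that footnote.

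Protocol 10.6.1 plans PD summaries "including the ratio to baseline for each treatment along with their associated confidence intervals". SAP 6.8.1 does not mention the ratio and refers further PK/PD detail to a separate SAP, but SAP 7 states that the analysis planned in the protocol has not changed. The post-lock addendum does not amend 5.1.2 or 5.1.3.

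**The concern.** A baseline rule should select the last measurement taken before the drug can act. When randomization and first dose fall on the same day, either anchor usually serves. It does not serve here for variables sampled only in one treatment class, because the site must know the allocation before it knows whom to sample. For those variables a cut-off at randomization excludes the sample that was meant to be the pre-treatment reference.

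What is at stake is the FXI ratio to baseline, which shows how far each abelacimab dose lowers free FXI. To a lesser degree, the same rule governs change from baseline for laboratory values and vital signs, since SAP 6.7.4 and 6.7.5 both refer to 5.1.2.

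**Working it through.** The plan gives no figure to reproduce, so the check applies the two rules to one sample.

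**Order of events on Day 1**
1. Randomization takes place on Day 1, the date of first dose (protocol 3.1.2 and 6.2).
2. The site contacts the IxRS before the first administration (protocol 6.2).
3. PK, FXI and ADA samples are taken only from patients assigned to abelacimab (Table 16-1). PK and ADA are drawn before dosing (protocol 5.5.1 and 5.5.3). Protocol 5.5.2 gives no such instruction for FXI, but FXI shares the PK row of the schedule.

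The ordinary sequence is therefore randomize, sample, dose. This follows from the footnote; the protocol does not state it outright.

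**The two rules applied to a sample drawn after randomization and before first dose**

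| Sample time | Randomization time | SAP 5.1.2 | SAP 5.1.3 | Last value before first dose |
|---|---|---|---|---|
| recorded | recorded | not baseline | screening/baseline | baseline |
| recorded | missing | baseline (deemed earlier) | screening/baseline | baseline |
| missing | recorded | baseline (deemed earlier) | screening/baseline | baseline |
| missing | missing | baseline (deemed earlier) | screening/baseline | baseline |

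The present wording accepts the sample in 3 of 4 cases; an anchor on first dose accepts it in 4 of 4. Two readings enter the table. The 5.1.2 exception is taken to apply when either time is missing. The pre-dose instruction for PK is taken to cover FXI where the sample is untimed.

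**Which row applies?** SAP 6.8 says "A listing of PK blood sample collection times and Plasma concentrations will be presented", so times exist for PK samples and plausibly for FXI in the same row. Neither document says whether a clock time of randomization is kept. The first row is plausible for FXI, but not established.

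**Upper bound for FXI.** Protocol 1.2.2 gives 1,287 randomized at 1:1:1. Abelacimab patients: 1,287 × 2/3 = 858. All would lose the FXI baseline only if every one had both times recorded and was sampled after allocation.

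**Variables also measured at screening.** Screening runs from Day -30 to Day -1 (protocol 3.1.1). A Day 1 hematology, PT/INR, aPTT or vital-sign value timed after randomization but before dosing is passed over for a screening value up to 30 days old. This can occur on rivaroxaban, where the first tablet is taken that evening (protocol 6.4.2). Nothing requires these assessments to follow the IxRS call, so the share is unknown.

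**Untimed values.** For an untimed Day 1 value with no instruction to collect before dosing or randomization, 5.1.2 deems it pre-randomization, whereas the last clause of 5.1.3 assigns it to the Treatment Period. The sections need reconciling here too.

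**The case against.** The strongest reply is that 5.1.2 and 5.1.3 should be read together. 5.1.2 rescues untimed samples, 5.1.3 places a Day 1 pre-dose sample in the screening/baseline period, and any sensible programmer would use it. The detailed PK/PD work belongs to a separate SAP that may define its own baseline, and the FXI and aPTT covariates in protocol 10.6.3 are also left to a separate plan. This narrows the point but does not remove it. 5.1.3 assigns data to periods and does not redefine the baseline value, and the 5.1.2 exception stops applying once times exist. A separate PK/PD plan would not alter the laboratory and vital-sign tables that rely on 5.1.2.

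A reader might go further and infer that PK, FXI and ADA have no baseline and that no PD ratio can be computed. The documents do not support that:
- aPTT is a PD variable and is drawn at screening in all patients, so its ratio always has a denominator.
- For FXI the failure depends on both times being recorded.
- No change from baseline is planned for PK. ADA is summarized as observed values by visit (SAP 6.9), so the Day 1 result stays in the data. SAP 2.8 speaks of patients who develop ADA, which implies a pre-dose reference, but 5.1.2 does not remove that sample.

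Nor can one conclude that a Day 1 aPTT or INR is free of earlier anticoagulants. Table 3-1 puts the last DOAC dose about 12 to 24 hours before study drug and has VKA patients randomized once the INR is below 2.5. Re-anchoring gives a more recent value, not necessarily a clean one.

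**Conclusion.** The point holds as a conditional defect of definition. With both times recorded, 5.1.2 read literally rejects the only pre-treatment FXI sample and contradicts 5.1.3, leaving the planned free/total FXI ratio without a denominator unless the separate PK/PD SAP provides one. For hematology, PT/INR, aPTT and vital signs the consequence is at most an older baseline.

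The conclusion rests on three assumptions: the footnoted samples are drawn after allocation, randomization times are captured, and the separate PK/PD SAP, not available here, sets no baseline of its own. The pre-dose samples exist whichever rule is used, and the primary and secondary bleeding analyses do not use a baseline value of these variables. The change is worth making because a stated rule can give a wrong result and is easily put right, not because the trial's main conclusions are at risk.

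**What to change.** In SAP 5.1.2, define baseline as the last non-missing value collected before the first dose of study treatment. Give untimed Day 1 values one rule in both sections: pre-dose where the protocol requires pre-dose collection, with the remaining untimed values handled as 5.1.3 prescribes. State explicitly that Day 1 FXI samples are pre-dose. Name the Day 1 pre-dose sample as the reference for ADA that develop on treatment, and make the separate PK/PD SAP use the same baseline.

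The cost is a sentence or two of text, one derivation in the programs, and a rerun of the change-from-baseline tables for laboratory values and vital signs. No new data are needed. The database is already locked, so the change belongs in the SAP addendum, marked as post-lock. If the programs already use the last pre-dose value, only the text needs correcting.

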### 5.1.3. Treatment Period

Data collected on the day of first dose will be assigned to the Treatment Period if the time (HH:MM) of data collection and time (HH:MM) of first dose of treatment are both recorded, and the data collection time is on or after the time of first dose of treatment. Otherwise, the assessment will be assigned to the screening / baseline period. If the time (HH:MM) of data collection is not recorded but the protocol and / or eCRF includes an instruction to the effect that all Day 1 assessments are to be performed prior to the first dose of treatment or randomization, the data collected at Day 1 will be assigned to the screening / baseline period, otherwise it will be assigned to the Treatment Period.

The Treatment Period is defined as the period from the date of the first dose of treatment up to and including the EoT date as defined in Section 3.1.

### 5.1.4. Visit Windows

All data will be analyzed using nominal study visit as defined in the Study Schedule and eCRF. No visit windows will be applied for summary and analysis unless specifically stated otherwise. For lab, data collected next month after missed scheduled visit (e.g., data collected at month 4 for missed month 3 visit) will be used for by-visit analysis.

## 5.2. Handling of Dropouts, Missing Data, and Outliers

### 5.2.1. Handling of Missing Primary Endpoint Data

Missing primary endpoint data will not be imputed.

### 5.2.2. Handling of Missing Safety Data

In general, missing clinical laboratory data, vital signs, and ECG data will not be imputed. Adverse event imputations for missing severity or relationship are given in Section 6.7.3. Unknown or partial medication and AE date imputations are given below and to be used only for the assessment of prior / concomitant status for medications and treatment-emergent status for AEs.

### 5.2.3. Handling of Partial and Missing Dates for Date of Birth, Adverse Events, Prior / Concomitant Medications

#### Missing or Partial Adverse Event and Prior / Concomitant Medication Start Dates

Missing and / or incomplete dates for medications and AEs are imputed in a manner resulting in the earliest onset or the longest duration during the Treatment Period, whilst ensuring that

the start date does not occur after the stop date. The stop date will not be imputed if the medication or AE is “Ongoing”. Technically, this will be done as follows:

For a missing / incomplete start date / time the earliest date / time of the following will be imputed:

- The later date of: the earliest possible start date / time, and the date / time of first dose of treatment.
- The latest possible start date / time.
- The latest possible stop date / time.

For a missing / incomplete stop date / time the later date / time of the following will be imputed:

- The earlier date / time of the latest possible stop date / time and the date / time of last dose of treatment.
- The earliest possible stop date / time.
- The earliest possible start date / time.

Here, the earliest possible date / time is defined as:

- The date / time itself if available.
- The date / time of the first day of the month at 00:00hrs, if month and year are available but the day / time is missing.
- The date / time of the first day of the year at 00:00hrs, if year is available but day / time and month are missing.
- 00:00hrs on the day of informed consent, if the date / time is completely missing.

The latest possible date / time is defined as:

- The date / time itself if available.
- The date / time of the last day of the month at 23:59hrs, if month and year are available but the day / time is missing.
- The date / time of the last day of the year at 23:59hrs, if year is available but day / time and month are missing.
- 23:59hrs on the date of last known date in the study for the patient plus one day, if the date / time is completely missing.

**5.2.4. Handling of Plasma Concentrations that are Below the Lower Limit of Quantification**

Plasma concentrations that are below the lower limit of quantification (BLQ) will be set to half of the value between BLQ and 0 for the calculation of summary statistics.

## 6. Statistical Methods

### 6.1. General Principles

All data processing, summarization and analyses will be performed using Fortrea's SAS Environment / Version 9.4 (or later) of the SAS® statistical software package.

The default summary statistics for quantitative variables will be the number of observations (n), mean, standard deviation (SD), median, 25th and 75th percentile, minimum (min) and maximum (max), for those patients with data.

All summary statistics will be rounded (using the SAS® function ROUND) and presented to one more decimal place than the raw value, except for the minimum and maximum values that will be presented with the same decimal precision as the raw value.

For qualitative variables, the number (n) and percentage (%) of patients with non-missing data per category will be the default summary presentation, and where appropriate and present, the number of missing values as a “Missing” category. Number of patients in the analysis population will be used as denominator for percentages calculation, unless stated otherwise in Tables, Figures and Listings (TFLs) mock shell(s).

All statistical comparisons will be made using two sided tests at the  $\alpha=0.05$  significance level unless specifically stated otherwise. All null hypotheses will be of no treatment difference. All alternative hypotheses will be two-sided.

All laboratory test results will be received from the central laboratories, and the results will be provided in both International System of Units (SI) units and conventional units. For the TFLs, the results will be summarized or presented in SI units.

Specifications for table, figures and data listing formats can be found in the TFL shells specifications for this study.

### 6.2. Patient Disposition and Data Sets Analyzed

Patient disposition will be summarized by treatment group and overall, where appropriate, for the All Screened Set. The following information will be reported:

- Number of patients for the following categories:
  - Screened,
- Number and percentage of patients for the following categories:
  - Randomized,

- Treated,
- Not Treated,
- Completed the study,
- Discontinued the Study,
- Reasons for study discontinuation.
- Number and percentage of patients included in each study population;
- Number and percentage of patients who completed / discontinued treatment, including the reasons for treatment discontinuation;
- Number and percentage of patients who met / did not meet all eligibility criteria, together with the criteria not met;
- Number and percentage of patients who failed screening prior to randomization, including the primary reason for screen failure;
- Number and percentage of patients at each site;

A patient will be regarded as having completed the study if the status recorded on the End of Study eCRF form is Complete. A patient will be considered as having discontinued the study if they have a eCRF status of premature study discontinuation.

A listing of all patients with their treatment and study completion status, including the respective reasons for treatment and study discontinuation will be presented for the ITT Set.

A listing of all screen failed patients with their reasons for screen failure including failing at least one inclusion / exclusion criteria will be presented for the All Screened Set.

### **6.3. Protocol Deviations**

All important protocol deviations leading to exclusion from the PPS will be summarized for the On-Treatment analysis set by treatment group and overall as described below:

- The number of unique patients with at least one important protocol deviation which led to exclusion from the PPS as well as the number of patients in each important protocol deviation category will be presented by default descriptive summary statistics for categorical variables.

A listing of all patients with one or more important protocol deviations will be presented for the On-Treatment analysis set.

## 6.4. Demographic and Other Baseline Characteristics

### 6.4.1. Demographic Characteristics

Demographic characteristics will be summarized for the On-Treatment Analysis Set by treatment group and overall as described below. All missing data will be presented as part of a missing category, if appropriate. Standard descriptive statistics will be presented for the continuous variables of:

- Age (years)
- Height (cm) at screening visit
- Weight (kg) at screening visit
- Body mass index (kg/m^2) at screening visit
- Body Temperature (degrees Celsius) at screening visit
- Systolic Blood Pressure (SBP [mmHg]) at screening visit
- Diastolic Blood Pressure (DBP [mmHg]) at screening visit
- Pulse Rate (beats per minute [bpm]) at screening visit

Total counts and percentages of patients will be presented for the categorical variables of:

- Age group (years):
  - < 65
  - 65 - 74
  - ≥75
- Sex
- Race
- Ethnicity

Demographic characteristics will be listed for the On-Treatment Analysis Set.

### 6.4.2. Baseline Characteristics

Baseline characteristics will be summarized for the On-Treatment Analysis Set by treatment group and overall as described below. All missing data will be presented as part of a missing category, if appropriate.

Total counts and percentages of patients will be presented for the categorical variables of:

- Stratification factors: the use of concomitant antiplatelet use at baseline (yes/no) and renal function ( $\text{CrCl} \leq 50 \text{ ml/min}$  or  $\text{CrCl} > 50 \text{ ml/min}$ ).
- Targeted medical background
  - Pattern of atrial fibrillation
  - Average weekly alcohol intake
  - History of heart failure
  - Most recent left ventricular ejection fraction
  - Hypertension
  - Diabetes mellitus
  - History of carotid artery disease
  - Peripheral arterial disease
  - Coronary artery disease
  - Myocardial infarction
  - History of bleeding
  - History of Gastrointestinal (GI) bleeding
  - Prior Cerebrovascular Disease
  - Prior Cerebrovascular Disease (Yes/No)
  - Associated hemorrhagic conversion
- Baseline medications
  - Currently taking any Aspirin Therapy
  - Aspirin Therapy frequency
  - Continue aspirin after randomization
  - Aspirin most frequently used
  - Currently taking any P2Y12 inhibitor
  - P2Y12 inhibitor type
  - P2Y12 inhibitor frequency
  - Continue P2Y12 inhibitor after randomization
  - Currently taking any antiplatelet therapy (other than Aspirin and P2Y12 inhibitor)
  - Currently taking an anticoagulant

- Anticoagulant
- Currently taking any oral or IV/IM NSAID (non-steroidal anti-inflammatory drug including COX-1 and COX-2 inhibitors) either prescription or non-prescription (Do not include Aspirin in this category)
- Received anticoagulation therapy for  $\geq 60$  days consecutively at any time in their life

Standard descriptive statistics will be presented for the continuous variables of targeted medical background:

- Days of most recent episode of atrial fibrillation to randomization date, which will be calculated as (randomization date - date of most recent episode of atrial fibrillation)
- Days of Prior Cerebrovascular Disease to randomization date, which will be calculated as (randomization date - date of Prior Cerebrovascular Disease)

Standard descriptive statistics will be presented for the continuous variables of baseline medications:

- Aspirin Therapy Dose (mg)
- P2Y12 inhibitor Dose (mg)

No formal tests of statistical significance will be performed on the demographic and baseline characteristics data.

Baseline characteristics will be listed for the On-Treatment Analysis Set.

